## 8.2 POTENTIAL PROBLEMS, MITIGATIONS AND EXPECTED RESULTS

We and others have already established the feasibility of obtaining DNA, proteomics and metabolomics datasets from LMIC settings (e.g.[4-6, 76, 108]). With the outstanding facilities available at AKU, we are therefore confident we will generate these datasets. In the unlikely event we find RNA yields are poor, we will revert to performing whole shotgun DNA sequencing (metagenomics), which also has the capacity to provide functional insights.

Our expectation is that: 1) study participants exhibiting positive maternal health and birth outcomes will be associated with more diverse communities than those exhibiting poor maternal health and/or birth outcomes; 2) pregnancies associated with poor nutritional status at the start of pregnancy, will exhibit a greater incidence of dysbiosis (e.g. loss of microbial diversity and decrease in otherwise dominant stool taxa e.g. Firmicutes and/or Bacteroidetes) throughout pregnancy; 3) pregnancies associated with pathogen exposure will result in dysbiosis; and 4) poor nutritional health will correlate with altered fecal metabolite profiles and changes in the expression of metabolic *pathway* enzymes encoded by the microbiome. Since analysis of microbiome data is a rapidly evolving field, to ensure data analysis is in line with best practices, we will adopt current state of the art bioinformatics tools for sequence processing, assembly, annotation and analysis. In case of delays or other issues that may be experienced at the Metabolomics Innovation Centre, we may rely on the SPARC Biocentre, hosted by the Hospital for Sick Children, to perform equivalent analyses.

As previous[39], we may expect specific taxa (prokaryotic or eukaryotic) will directly correlate

with nutritional status during pregnancy and birth outcomes. The core deliverables will be an unprecedented view of dynamic changes in microbial communities that contribute to nutritional status during pregnancy, together with the prediction of biochemical pathways and taxa responsible.

## 9 STATISTICAL CONSIDERATIONS

### 9.1 POWER CALCULATION

The adequacy of the sample size was verified using the ‘pwr’ package (version 1.2-2) in R (version 3.6.1). Calculations were based on the correlation between  $\alpha$ -diversity (Shannon index) and weight gain during pregnancy. Assuming 400 participants are recruited into the study, and a type I error rate of 0.05, there will be 80% power to detect a correlation coefficient ( $r$ )  $>0.14$ . This is conventionally considered a small effect size[109]. Thus, we expect to be powered to reveal significant association between weight gain during pregnancy and diversity. Further, a study of 123 lean and 24 obese individuals, revealed 96% power to detect differences in Bacteroidetes abundance and 80% power for Firmicutes[110], while a cohort of 44 Malawian malnourished children was sufficient to detect significant differences in bacterial  $\alpha$ -diversity in the presence and absence of *Blastocystis*.

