Objectives	
Primary Objective:
 
To assess if alterations of the microbiota in the maternal gut (dysbiosis) is associated with maternal gestational weight gain.
 
To determine the association between maternal microbiome dysbiosis during pregnancy and birth outcomes, infant growth, infant nutritional status and health in the first year of life.
 
Secondary Objectives:
 
To link the maternal microbiome to dietary intake, with a focus on calories and macronutrients.
 
To integrate maternal anthropometric factors, morbidity and mortality with microbiome data to reveal key modulators (microbial taxa and metabolites) of dietary intake during pregnancy and the post-partum period.
 
To determine the impact of the maternal microbiome during pregnancy, including the exposure to pathogens and parasites, on the development of the infant microbiome.
 
To investigate the maternal microbiome's exposure to pathogens and parasites, and the association with intestinal inflammation.
 
Exploratory Objectives:
 
To explore the role of the maternal gut microbiome during pregnancy and to identify gut community dynamics in pregnant women and how this impacts differences between dietary intake and nutritional status.
 
To investigate socio-economic factors; including gender, poverty, exclusion and empowerment, and their influence on the health of a mother's microbiome (assessed by alpha and/or beta diversity, and absence of pathogens).
 
To explore the role of the human microbiota on nutritional status by performing fecal microbiota transplants in germ free mice and sterile piglets.

Recruitment and Follow-up	

1) MV1: 10-14 weeks post conception

2) MV2: 30-34 weeks post conception

3) MV3/ IV1: 24-72 hours after birth

4) MV4/IV2: 3 months post-partum

5) MV5/ IV3: 6 months post-partum

	6) MV6/IV4:12 months post-partum  MV: Maternal Visit IV: Infant Visit
Study Population:	Pregnant, married women aged 17 to 24 years from the Matiari district, Pakistan and their infants.
No. of Subjects	400 women and their infants. • 200 subjects with normal BMI (18.5-24.9) at conception • 200 subjects with low BMI (less than 18.5) at conception
Study Duration:	The study duration will be approximately 3 years.

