### 3 STUDY OBJECTIVES

**Table 4: Study Objectives**

OBJECTIVES	ENDPOINTS	JUSTIFICATION FOR ENDPOINTS
Primary		
To assess if alterations of the microbiota in the maternal gut (dysbiosis) is associated with maternal gestational weight gain.	The primary endpoint will be maternal gestational weight gain (GWG) during pregnancy, measured between the first (10-14 weeks post-conception) and second time point (30-34 weeks post conception).  To monitor microbiome dynamics, 16S and 18S rDNA surveys will be	Weight gain is a key predictor of adverse birth outcomes[83, 84].

OBJECTIVES	ENDPOINTS	JUSTIFICATION FOR ENDPOINTS
	
applied to the maternal stool samples to monitor the bacterial and eukaryotic components of the microbiome.
	
To determine the association between maternal microbiome dysbiosis during pregnancy and birth outcomes, infant growth, nutritional status and health status in the first year of life.	
The specific birth outcomes evaluated will include preterm birth, birth weight, SGA, LGA, head circumference at birth, mortality, morbidity.
 
The specific infant outcomes evaluated will include the following growth and nutritional status parameters; WHO z-scores for weight, length, head circumference and MUAC during the first year.
 
Birth characteristics will be collected, including information on vaginal or cesarean birth (elective, emergency), placental insufficiency and antibiotic usage.
 
Infant morbidity and mortality will be assessed at follow-up visits, with questions regarding care-seeking, hospitalizations and treatments for any morbidity; including antibiotic usage.
 
For the infants an assessment of amount and mode of feeding will be obtained at 3-months, 6-months and 12-months.
 
To monitor microbiome dynamics, 16S and 18S rDNA surveys will be applied to the maternal stool samples to monitor the bacterial and eukaryotic components of the microbiome.
	
This will allow for an examination of the association between the maternal microbiome and birth outcomes.

Secondary		
To link the maternal microbiome to dietary intake, with a focus on calories and macronutrients.	
The maternal participants will complete a 24 hour dietary recall at both time points during pregnancy and at 1-year post-partum.
	
Quantitative measures of nutritional status will provide parameters to better inform microbiome analyses.

OBJECTIVES	ENDPOINTS	JUSTIFICATION FOR ENDPOINTS

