### 4.2 STUDY DESIGN

The study will be a prospective, longitudinal observational study to investigate the impact and relationship between prokaryotic and eukaryotic microbes in the gut and their association with maternal health and birth outcomes among young women, 17-24 years of age in Matiari District, Pakistan. The study will aim to recruit 400 women into two groups based on BMI at time of recruitment (Normal: BMI between 18.5 and 24.9 kg/m^2 and Low: BMI less than 18.5 kg/m^2, as defined by WHO guidelines[85]). Our goal is to recruit 200 participants with normal BMI and 200 participants with low BMI into the study. However, in the event that we have difficulty reaching this recruitment target, we will recruit more women into the normal weight BMI. The study will follow women and their infants over the course of their pregnancy and for a year post-partum, collecting stool and blood samples, nutritional information, health assessments, anthropometric measurements and empowerment metrics at different time points.

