## 5.4 STRATEGIES FOR RECRUITMENT AND RETENTION

This study builds off the MaPPS trial partnership between Aga Khan University in Pakistan and [name] at SickKids. Led by Principal Investigator [name], this trial is an exciting partnership between SickKids' Centre for Global Child Health and the Institute for Global Health and Development, AKU. Here we will leverage the clinical network established by the MaPPS trial, to extend the trial to recruit hundreds of young mothers to investigate host-microbiome interactions in pregnancy.

The study will aim to recruit 400 married women into two groups based on BMI at time of recruitment (Normal: BMI between 18.5 and 24.9 kg/m^2 and Low: BMI less than 18.5 kg/m^2, as defined by WHO guidelines[85]). Our goal is to recruit 200 women with normal BMI and 200 women with low BMI. However, in the event that we are unable to reach this recruitment target, we will recruit more women in the normal BMI category. With an annual birth rate of 2% and Matiari Surveillance data revealing proportions of normal and low BMI individuals to be 49.7% and 29.8% respectively, we anticipate meeting our target sample size in the first year of the study.

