### 6 DISCONTINUATION AND WITHDRAWAL

Participants are free to withdraw from participation in the study at any time upon request. An Investigator may discontinue or withdraw a participant from the study for the following reasons:

- Withdrawal of informed consent (participant can withdraw for any reason)

- If any clinical Adverse Event (AE), laboratory abnormality, or other medical condition or situation occurs such that continued participation in the study would not be in the best interest of the participant.
- Significant study non-compliance
- If the participant meets an exclusion criterion (either newly developed or not previously recognized) that precludes further study participation

The reason for participant discontinuation or withdrawal from the study will be recorded in the study file. The data from participants who are withdrawn or discontinued from the study will be used in the analysis unless the participant requests otherwise.

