#### 9.4.1 ADDRESSING THE PRIMARY OBJECTIVES

This study has two primary objectives: 1) To assess if alterations of the microbiota in the maternal gut (dysbiosis) are associated with maternal gestational weight gain; and 2) To determine the association between maternal microbiome dysbiosis during pregnancy and birth outcomes, infant growth, nutritional status and health status in the first year of life.

The first objective will be addressed through the following approaches. First, maternal gut bacteria and eukaryotic profiles will be used to calculate Bray-Curtis dissimilarity metrics between individual samples which will be leveraged in principal co-ordinate analyses to determine the extent samples collected at the first or third trimester, exhibiting similar gestational weight gains, co-cluster. Permutational multivariate analysis of variance (PERMANOVA) tests will assess the degree of overlap between samples exhibiting low gestational weight gain versus samples exhibiting high gestational weight gain. A lack of clustering in the first trimester, followed by clustering of samples on the basis of similar gestational weight gain would indicate that alterations in the maternal microbiota during the course of pregnancy, impacts gestational weight gain. Next, we will attempt to correlate changes in the alpha diversity (as measured by the Shannon and Simpson indices) of the gut microbiome samples between the first and third trimester, with gestational weight gain. A decrease in alpha diversity (indicative of dysbiosis) associated with low gestational weight gain, would again indicate that dysbiosis is associated with maternal weight gain. To examine the influence of individual taxa on gestational weight gain, we will perform bivariate analyses that examine the correlation (Pearson, Spearman) of each taxon with gestational weight gain. Correlations will examine taxon abundance in first and third trimester, in addition to the change in abundance between the two trimesters. The Benjamini-Hochberg procedure will be applied to correct p-values while controlling for false-discovery rates.

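### Section 9.1 counts the 400 women recruited as the number analysed, so its detectable correlation of 0.14 is a best case

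*Protocol*

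**What the plan says.** Section 9.1 takes the study size as given and checks it; it opens with "The adequacy of the sample size was verified using" the R package pwr. The check concerns the correlation between alpha-diversity (Shannon index) and weight gain in pregnancy: "Assuming 400 participants are recruited into the study, and a type I error rate of 0.05, there will be 80% power to detect" a coefficient above 0.14. The section calls this a small effect and expects the study to be adequately powered for the association.

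The same 400 is the enrolment target throughout. The synopsis gives "400 women and their infants", section 4.2 says "The study will aim to recruit 400 women into two groups based on BMI at time of recruitment", and section 5.4 says "Our goal is to recruit 200 women with normal BMI and 200 women with low BMI".

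Table 4 of section 3 defines the primary endpoint as gestational weight gain, "measured between the first (10-14 weeks post-conception) and second time point (30-34 weeks post conception". Section 9.4.1 plans to correlate weight gain with "changes in the alpha diversity (as measured by the Shannon and Simpson indices) of the gut microbiome samples between the first and third trimester".

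On loss, section 6 says "Participants are free to withdraw from participation in the study at any time upon request". Section 6.1 covers missed visits and loss to follow-up, section 6.2 covers women who move away, and section 7.4 lists miscarriage, abortion and stillbirth among the events to be monitored. The protocol gives no loss rate, no inflation factor and no expected number of women with complete data.

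**The concern.** Power depends on the women who enter the analysis, not on those who enrol. A woman with no weight at MV2 has no value for the primary endpoint and drops out of the correlation. For the planned change-in-diversity analysis she also needs stool from both visits. Because 400 is both the recruitment target and the number in the power calculation, no surplus covers loss over the 16 to 24 weeks between the two visit windows (30 − 14 = 16; 34 − 10 = 24).

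This is the only power figure calculated for this study's own primary endpoint. It assumes complete data from every woman but is offered as what the study can expect. What is at stake is the accuracy of that figure. The r of 0.14 is what a sample of 400 yields, not a stated target effect, so the consequence of loss is a somewhat larger detectable correlation.

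**Working it through.** **Inputs.** From 9.1: n = 400, type I error 0.05, power 80%, r = 0.14. Sidedness is not stated. A two-sided test reproduces the printed figure. A one-sided test does not: it gives a detectable r of 0.124 and 87.8% power at r = 0.14. The loss rates below are assumptions, because the protocol gives none.

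**Formula (pwr's correlation test, two-sided).** With t the 0.975 quantile of Student's t on n − 2 degrees of freedom:

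- critical correlation: r_c = √[t² / (t² + n − 2)]
- transformed effect: z_r = atanh(r) + r / [2(n − 1)]
- power = Φ[(z_r − atanh r_c)·√(n − 3)] + Φ[(−z_r − atanh r_c)·√(n − 3)]

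**Step 1: reproduce the protocol's figure.** At n = 400, t = 1.9659, r_c = 0.0981 and atanh r_c = 0.0984. For r = 0.14, z_r = 0.1411. The first term is Φ(0.851) = 0.803 and the second is negligible, so power is 80.3%. The r with exactly 80% power is 0.1395. The plain Fisher formula agrees: tanh[(1.960 + 0.842)/√397] = 0.1397. The 0.14 in 9.1 is therefore correct for 400 complete women.

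**Step 2: find the margin.** Solving for n at r = 0.14 gives 397.3, so 398 women. Power is 80.07% at 398 and 79.97% at 397. The margin is 400 − 398 = 2 women.

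**Step 3: apply assumed losses.**

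| Women without complete MV1 and MV2 data (assumed) | n analysed | r detectable with 80% power | r² | Power at r = 0.14 |
|---|---|---|---|---|
| 0% | 400 | 0.140 | 1.9% | 80.3% |
| 5% | 380 | 0.143 | 2.0% | 78.2% |
| 10% | 360 | 0.147 | 2.2% | 76.0% |
| 20% | 320 | 0.156 | 2.4% | 71.0% |

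**Step 4: allow for rounding.**

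- Power at r = 0.14 still rounds to 80% at 393 women (79.6%). It is 79.5% at 392, a 2% loss.
- The detectable r still rounds to 0.14 at 371 women (0.1448), a loss of 29/400 = 7.25%. At 370 it is 0.1450 and rounds to 0.15.
- A restated r of 0.15 would need 346 complete women, so it would hold up to a loss of 54/400 = 13.5%.

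**The case against.** The strongest reply is that nothing in 9.1 is miscalculated. The sentence is openly conditional on 400 women, it verifies a fixed size, and its conclusion that a small correlation is detectable survives at every loss rate tabulated. At 5% loss the detectable r still prints as 0.14 to two decimals. The change becomes visible at that precision only above about 7% loss, and no rate is documented on either side of that. All of this is correct, and it is why the point is minor. Because 0.14 is not a target, the drop in power at exactly 0.14 should also carry less weight than the shift in detectable r.

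A second reply is that only loss between MV1 and MV2 counts, while sections 6 to 6.2 and 7.4 cover the whole study up to 12 months after delivery. The protocol also limits early loss. It excludes women who intend to leave the area (5.2), enrols at about 10 to 14 weeks (5.4.1), makes most visits at home (7.3), reschedules missed visits and makes repeated contact attempts (6.1), and requires stool samples (2.3). Section 6 keeps data from women who withdraw. These provisions reduce loss but do not make it zero, and retained data cannot supply an MV2 weight that was never taken.

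A third reply is that 9.1 refers to Shannon diversity without saying change in diversity, so it may need stool from one visit only. That reading is possible. The MV2 weight is needed either way, so the point does not depend on it.

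**Conclusion.** The concern holds, as a minor one. Section 9.1 gives the power for 400 complete women but words it as the power from recruiting 400, with a margin of two women and no allowance for loss. At assumed losses of 5% to 20%, the detectable correlation is 0.143 to 0.156 rather than 0.140, and the variance explained is 2.0% to 2.4% rather than 1.9%. These figures rest on a two-sided 0.05 test and on loss rates that the protocol does not supply. They do not show that the study is underpowered or that 400 is the wrong number.

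**What to change.** Restate the sentence in 9.1 for the number of women expected to have complete MV1 and MV2 data, using the investigators' own expected loss at this site, and say that the test is two-sided. As an illustration, with an assumed 5% to 20% range to be replaced by their figure: *Assuming 400 women are recruited and 5% to 20% lack complete MV1 and MV2 data, 380 to 320 women give 80% power (two-sided 0.05) to detect r of about 0.143 to 0.156.*

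The cost is one sentence and a slightly larger stated r. Recruitment, visits and analyses stay as they are.

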### 9.2 SUBGROUP ANALYSIS

To reduce study complexity and to avoid confounding effects due to micronutrient deficiencies, we will focus specifically on interactions between macronutrient deficiencies with host microbiome and health. Given the high prevalence of micronutrient deficiencies experienced within the study population, the effect of micronutrient deficiencies of public health importance (i.e. anemia, iron deficiency, iron deficiency anemia, vitamin A deficiency and vitamin D deficiency) will be explored within a subgroup analysis. We will achieve this by monitoring for anemia as well as serum mineral content when participants are recruited into the study.

### 9.3 STATISTICAL ANALYSIS

We will work with the research core in Calgary to apply multivariate analyses and other integrative methods to analyze microbiome data in the context of patient nutritional status and health outcomes. Our initial strategy is to apply the Similarity Network Fusion framework[111] to combine the various datatypes (i.e. metabolomics, microbiome, and clinical). In this approach networks are first constructed from each datatype, with nodes representing patients and links representing similarities between participants (e.g. based on correlations between microbiome or metabolite profiles). Networks are then fused using a method based on message-passing theory to identify links shared between patients supported by multiple datatypes, eliminating poorly supported links and strengthening links supported by multiple datatypes. This allows the integration of all available datasets to uncover their global substructures that can be associated to relevant outcomes. In an alternative approach, we will also employ Random Forests to identify combinations of predictors (microbial and/or metabolic factors) that best correlate with our clinical outcomes. Beyond integrative methods we will also apply simple statistical tests (e.g.

Wilcoxon, t-test, Spearman's rank correlation, PERMANOVA) to examine pairwise interactions (e.g. presence of pathogens vs. bacterial diversity and/or abundance of specific taxa; metabolic pathway expression vs. inflammation; and stool metabolites vs. serum metabolites). Further, we will also attempt to include additional quantitative measures of nutritional status as well as gender-related variables from the empowerment questionnaires, as covariates where appropriate. These analyses will reveal relationships between taxonomic composition, microbiome diversity (both prokaryotic and eukaryotic), metabolomics and the primary and secondary outcome measures gathered.

#### 9.4 PLAN FOR STATISTICAL ANALYSIS

The following details the plans for evaluating the aims of this study. Table 8 lists the variables to be considered in the analyses.

Table 8. List of variables collected in the study to be utilized in analysis

##### **Clinical Variables**

1. Maternal BMI, MUAC and SFT (continuous variables)
2. Maternal gestational weight gain (continuous)
3. Maternal markers of inflammation (continuous)
4. Infant sex
5. Infant morbidity and mortality
6. Infant weight, height, head circumference (continuous)
7. Infant gestational age
8. Infant birth weight, Kg (continuous)
9. Breastfeeding duration (continuous)
10. Maternal age years
11. Maternal use of antibiotics
12. Infant use of antibiotics
13. Maternal calorie and macronutrient intake
14. Maternal incidence of pathobionts
15. Infant incidence of pathobionts

##### **Microbiome Variables**

1. Maternal gut bacteria profile
2. Maternal eukaryotic microbe profile
3. Infant gut bacteria profile
4. Infant eukaryotic microbe profile
5. Maternal metabolomic profile of stool
6. Maternal metabolic pathway expression profile
7. Maternal bacterial gene expression profile

